3.2. General Overview of Analyses

3.2.1. Statistical Methods

The study outcomes will be summarized by treatment group. Descriptive summary statistics including number of patients, mean, median, standard deviation, standard error of mean, 25th percentile, 75th percentile, minimum, and maximum for continuous variables, and counts and percentages for categorical variables will be provided to summarize most data. The efficacy endpoints will be assessed on the full analysis set (FAS) and per-protocol set (PPS) with the latter being the basis for the primary efficacy analysis. The safety analyses will be performed on the Safety Set. Pharmacokinetic analysis will be conducted in the PK Set.

All planned analyses will compare each ISIS 757456 treatment group to pooled placebo.

All statistical tests will be conducted using 2-sided tests with 5% Type I error rate unless otherwise stated. P-values will be provided to assess the null hypothesis that there is no statistical difference between an ISIS 757456 treatment group and pooled placebo in study endpoints. The stratification factor (screening eGFR status [<60 vs. ≥ 60 mL/min/1.73 m²]), treatment received, and baseline measure are included in the Analysis of Covariate (ANCOVA) model as independent variables. For the continuous endpoints, the ANCOVA model will be applied or Van Elteren test with treatment and randomization stratification factor if the data departs substantially from normality. The normality assumption will be assessed by the Shapiro-Wilk test based on the residuals from ANCOVA modeling. Least Square mean (LSM) difference with 95% CI and p-values between treatment groups in study endpoints will be provided based on ANCOVA model. For the dichotomous endpoints, logistic regression model with treatment, randomization stratification factor and baseline measure (SBP) as independent variables will be used instead.

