3.4. Secondary Efficacy Analyses

3.4.1. Secondary Efficacy Endpoints

The secondary efficacy analyses will be performed using statistical methods described in Section 3.2.1. ANCOVA model will be used for continuous endpoints, logistic regression model will be used for dichotomous endpoints. Secondary endpoints include:

- 1. Comparison of percent change from baseline to Study Day 85 in AGT between an ISIS 757456-treated group and pooled-placebo in the PPS
- 2. Comparison of change from baseline to Study Day 85 in SBP from 24-hrs mean ABPM between an ISIS 757456-treated group and pooled-placebo in the PPS
- 3. Comparison of proportion of patients reaching the goals of seated automated office SBP \leq 140 mmHg and DBP \leq 90 mmHg at Study Day 85 between an ISIS 757456-treated group and pooled-placebo in the PPS, excluding patients with baseline SBP \leq 140 mmHg

- 4. Comparison of absolute value, change and percent change from Baseline to each scheduled post-Baseline visit in plasma AGT between each ISIS 757456-treated group and pooled-placebo group in PPS and FAS
- 5. Comparison of change from Baseline to Study Day 85 in SBP and DBP from 24 hr mean ABPM between each ISIS 757456-treated group and pooled-placebo group in the PPS and FAS
- 6. Comparison of patient incidence in reaching the goals of seated automated office SBP ≤ 140 mmHg, DBP ≤ 90 mmHg, and both for each scheduled, post-Baseline visit between each ISIS 757456-treated group and pooled-placebo group in PPS and FAS, excluding patients with Baseline SBP ≤ 140 mmHg
- 7. Comparison of patient incidence in reaching the goals of seated automated office SBP \leq 130 mmHg, DBP \leq 80 mmHg, and both for each scheduled, post-Baseline visit between each ISIS 757456-treated group and pooled-placebo group in PPS and FAS
- 8. Comparison of change from Baseline to each scheduled post-Baseline visit in seated automated office SBP between each ISIS 757456-treated group and pooled-placebo group in PPS and FAS
- 9. Comparison of change from Baseline to each scheduled post-Baseline visit in seated automated office DBP between each ISIS 757456-treated group and pooled-placebo group in PPS and FAS

Figures contain the summary (mean with standard error of mean) by scheduled visit overtime based on PPS will be provided. Spaghetti plots demonstrating each individual's efficacy assessment over time by treatment group will be provided.

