3.5. Exploratory Analyses

The exploratory efficacy analyses will be conducted using statistical methods described in Section 3.2.1. ANCOVA model will be used for continuous endpoints, logistic regression model will be used for dichotomous endpoints using PPS and FAS.

- Comparison of absolute levels, change and percent change from baseline to each scheduled post-Baseline visit in angiotensin II, renin (Plasma renin activity [PRA]; direct renin), and urinary AGT will be conducted between each ISIS 757456-treated group and pooled-placebo group in the PPS and FAS.
- Comparison of absolute scores, change from baseline to each scheduled post-Baseline visit in SF-12 scores (8 domains, PCS, and MCS), and EQ-5D-5L (5 dimensions, VAS, and index score) will be conducted between each ISIS 757456-treated group and pooled-placebo group.

- Proportion of non-worsening from baseline to each scheduled post-Baseline PGI-C and PGI-S will be compared between each ISIS 757456-treated group and pooled-placebo group. PGI-C will be categorized by non-worsening and worsening, where non-worsening includes categories of "Much better", "A little better" and "No change". PGI-S will be categorized by non-worsening and worsening, where non-worsening defined as ≥ 0 point improvement in the change from baseline score. The adjusted odds ratio (each ISIS 757456-treated dose group vs. pooled-placebo group) with 95% CI from logistic regression model will be provided.
- Comparison of change from Baseline to Study Day 85 in daytime SBP and DBP from 24 hr ABPM will be conducted between each ISIS 757456-treated group and pooled-placebo group
- Comparison of change from Baseline to Study Day 85 in nighttime SBP and DBP from 24 hr ABPM will be conducted between each ISIS 757456-treated group and pooled-placebo group
- Comparison of change from Baseline to Day 85 in eGFR will be conducted between each ISIS 757456-treated group and pooled-placebo group
- Comparison of change from Baseline to Day 85 in UACR will be conducted between each ISIS 757456-treated group and pooled-placebo group
- Primary endpoint, selective secondary and exploratory endpoints will be also analyzed using a sub-population of patients with Baseline 24 hr ABPM SBP > 130
- POP-HSQ scores will be listed.

Additional POP-HSQ summaries and analysis will be conducted, details are described in POP-HSQ SAP. Other exploratory PK endpoints will be further described in the Section 3.6.

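### Every logistic model in the SAP adjusts for baseline SBP, so the ungated DBP-only goals and exploratory PGI-S are not adjusted for their own baselines, although both are collected

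*Combined protocol and SAP*

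**What the plan says.** SAP 3.2.1 contains the only covariate specification for dichotomous endpoints: a "logistic regression model with treatment, randomization stratification factor and baseline measure (SBP) as independent variables". The ANCOVA sentence in the same section is generic: "treatment received, and baseline measure are included in the Analysis of Covariate (ANCOVA) model as independent variables". Only the logistic sentence ties the baseline to SBP.

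Two later sections use that logistic model.

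- **SAP 3.4.1:** "The secondary efficacy analyses will be performed using statistical methods described in Section 3.2.1". Item 6 opens with "Comparison of patient incidence in reaching the goals of seated automated office" and covers the SBP goal of 140 mmHg, then "DBP ≤ 90 mmHg, and both for each scheduled, post-Baseline visit between each ISIS 757456-treated group", with pooled placebo as the comparator. Item 7 does the same for 130 and 80 mmHg. Each item therefore includes a DBP-only goal at every visit.
- **SAP 3.5:** "The exploratory efficacy analyses will be conducted using statistical methods described in Section 3.2.1". For PGI-S, "PGI-S will be categorized by non-worsening and worsening, where non-worsening defined as ≥ 0 point improvement in the change from baseline score". Its treatment contrast is an odds ratio, which "with 95% CI from logistic regression model will be provided".

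Neither section names a different covariate. The protocol does not impose the SBP restriction: section 10.1 speaks generically of stratification factors and the baseline measurement, and section 10.6.3 names no covariates for the logistic model. The additional covariates that SAP 3.2.1 and 3.2.7 allow are optional and exploratory, and the list in 3.2.7 contains neither DBP nor PGI-S.

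**The concern.** A patient's chance of meeting a DBP goal depends heavily on the DBP at which that patient started. Baseline SBP stands in for this only as far as the two pressures correlate. For PGI-S, the outcome is a change from baseline on the five-point scale in SAP 3.2.8. A patient already in the worst category cannot worsen, so baseline PGI-S is prognostic by construction.

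The better covariates cost nothing to obtain. Protocol Appendix A schedules sitting SBP and DBP at screening and before dosing on Day 1, and PGI-S on Day 1. SAP 3.2.1 already defines baseline for both as the last non-missing value before the first dose. At stake are precision and the correction of chance baseline imbalance for the DBP-only goals and PGI-S.

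**Working it through.** **1. The plan's own figure.** SAP 3.3.2 gives 43 per group for a difference of 8 mmHg, SD 13, two-sided 0.05 and about 80% power. By the normal approximation, n = 2 × (1.960 + 0.842)² × 13² / 8² = 2 × 7.849 × 2.641 = 41.5, so 42. With the noncentral t, 42 gives 79.6% and 43 gives 80.5%, which reproduces 43. With 10% dropout, 43 / 0.9 = 47.8, so 48, against 150 / 3 = 50 planned. None of this depends on the present point. It only sets a realistic arm size.

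**2. Effect on the DBP-only goals.** The documents give no DBP variance, correlation or effect, so every input here is an assumption: 45 per arm, baseline DBP mean 88 and SD 10, placebo change −4, drug effect −5 mmHg, correlation r between baseline SBP and DBP, and correlation ρ between Day 85 DBP and its own baseline.

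Day 85 DBP = 88 − 4 − 5 × treatment + 10 × (ρ·d + √(1 − ρ²)·e), where d is standardised baseline DBP and e is standard normal noise. The logistic model contains treatment and stratum, plus either SBP (as in the SAP) or SBP and DBP. There were 2,000 simulated trials per row, so the Monte Carlo standard error of one power figure is at most √(0.25 / 2000) = 1.1 points.

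| Goal (mmHg) | r | ρ | SBP only | SBP + DBP | Gain (points) |
|---|---|---|---|---|---|
| DBP ≤ 80 | 0.2 | 0.5 | 46.5% | 52.3% | 5.8 |
| DBP ≤ 80 | 0.2 | 0.7 | 48.6% | 61.6% | 13.0 |
| DBP ≤ 80 | 0.5 | 0.5 | 44.5% | 48.9% | 4.4 |
| DBP ≤ 80 | 0.5 | 0.7 | 46.5% | 58.3% | 11.8 |
| DBP ≤ 90 | 0.2 | 0.5 | 35.4% | 39.8% | 4.4 |
| DBP ≤ 90 | 0.2 | 0.7 | 37.0% | 49.5% | 12.5 |
| DBP ≤ 90 | 0.5 | 0.5 | 35.9% | 38.8% | 2.9 |
| DBP ≤ 90 | 0.5 | 0.7 | 38.1% | 46.1% | 8.0 |

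With no drug effect, the rejection rate was 3.7 to 5.4% with SBP only and 4.3 to 5.5% with both covariates.

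**3. Sensitivity to ρ.** With 40 per arm, the same mean, SD and placebo change, and effect 5, the gain was 0.3 to 0.5 point at ρ = 0.3, about 2 at 0.4, 3 to 4 at 0.5 and 5 to 6 at 0.6. With mean DBP 86 and effect 6, it was about 1 point at ρ = 0.3 and 10 to 11 at 0.7. Restricting to baseline SBP above 140 mmHg, as item 6 does, with 43 per arm, ρ = 0.6, r = 0.5, mean DBP 82 to 90 and effect 4 or 6, gave 3 to 7 points.

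**4. Combined goal.** For SBP ≤ 140 and DBP ≤ 90 mmHg together, adding baseline DBP changed power by less than 1 point.

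**5. Chance imbalance.** In the runs restricted to SBP above 140 mmHg, each 1 mmHg of baseline DBP imbalance moved the log odds ratio by 0.07 to 0.11 with SBP as the covariate, and by −0.01 to 0.04 once DBP was added. The imbalance has SD 10 × √(2 / 43) = 2.2 mmHg. An imbalance of 2 mmHg therefore moves the odds ratio by a factor of exp(0.14) = 1.15 to exp(0.22) = 1.25 when DBP is left out.

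**The case against.** - **Drafting carry-over.** The SBP in brackets may have been carried over from the primary ANCOVA sentence in SAP 3.1, and protocol 10.1 is compatible with using each endpoint's own baseline. That is plausible, but a programmer following SAP 3.2.1 literally would fit SBP.
- **DBP is tested better elsewhere.** Item 9 of SAP 3.4.1 compares change in DBP by ANCOVA with the generic baseline. With SD 10, ρ = 0.6, 40 per arm and effect 6, the residual SD is 10 × √(1 − 0.36) = 8, the standard error is 8 × √(2 / 40) = 1.79, and power is about 91%. Under the same SD, ρ, arm size and effect (baseline SBP above 140 mmHg, r = 0.5, mean DBP 86), the DBP ≤ 90 goal has about 45% power with SBP only and 54% with DBP added. This stands: the loss falls on a less efficient view of the same data.
- **No controlled inference suffers.** SAP 3.4.2 controls the primary and the first three secondary endpoints. The DBP-only goals lie outside that sequence and PGI-S is exploratory. This also stands. A reader might infer that gated secondary 3 is weakened because it has a DBP component, but step 4 shows no gain from adding DBP.
- **The size is assumption-driven.** It is, and at ρ = 0.3 the gain is close to nothing.

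**Conclusion.** The point holds for the DBP-only goals in items 6 and 7 of SAP 3.4.1 and for PGI-S non-worsening in SAP 3.5. Their logistic models omit a baseline that the trial collects and that predicts the outcome better than SBP does. Under DBP SD 10 mmHg, ρ of 0.3 to 0.7, a DBP effect of 5 to 6 mmHg and about 40 to 45 per arm, none of which is in the documents, the cost is roughly 0 to 13 power points on the DBP-only goals. No figure is available for PGI-S, where the argument rests on how the outcome is defined.

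A reader might infer that these comparisons are biased or that false positives increase. The documents do not support that. Allocation is randomised, the imbalance is chance imbalance, and simulated type I error is near 5% with either covariate. PGI-C is not affected: Appendix A schedules it only at Day 85, so it has no baseline to omit. POP-HSQ is analysed under a separate SAP that was not available.

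**What to change.** Amend SAP 3.2.1 before any unblinding, including the optional interim analysis, to name the baseline covariate of each logistic model alongside treatment and the eGFR stratum:

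- SBP goals: baseline SBP.
- DBP-only goals (≤ 90 and ≤ 80 mmHg): baseline SBP and baseline DBP.
- PGI-S non-worsening: baseline PGI-S.
- PGI-C non-worsening: no own baseline exists, so keep treatment and stratum, with baseline SBP optional.
- Gated combined SBP ≤ 140 and DBP ≤ 90 mmHg goal: leave as it is, because adding DBP does not improve it.

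The cost is a few lines of SAP text, one extra covariate in the DBP-only models and a change of covariate for PGI-S. No new data are needed, and sample size and testing sequence do not change. Fixing the choice in advance also avoids a covariate decision made after the data are seen.

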3.4.3. Post-Treatment

Patients are to return to the Study Center for Post-Treatment visits on Study Days 85, 92, 106, 120, 148, and 169. The final study visit will be Study Day 169.

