To evaluate treatment difference across scheduled post-baseline visits, an additional mixed model with repeated measures (MMRM) analysis may be utilized. Besides stratification factor, visit, treatment received, baseline measure, and treatment-by-visit interaction will be included in the model, which visit as an ordinally categorical variable. An unstructured covariance will be used initially, with correlation coefficients being greater for visits that are closer. Other covariance structures, such as first-order autoregressive covariance structure based on the assumption of the measurements over time are expected to be correlated, may be considered based on model fitting consideration. The adjusted mean with 95% CI for each treatment group and 95% CIs for the mean difference between pooled placebo and each ISIS 757456 treatment groups at each scheduled time point will be provided.

Additional covariates, such as baseline characteristics, may be considered as an additional covariate in the comparison statistical modeling and for subgroup summary for the exploratory analysis purpose.

Laboratory outcomes with lower limit of quantitation (LLQ) or less will be imputed as LLQ in the summary tables and figures.

PK parameters will be summarized using include number of patients, mean, standard deviation, coefficient of variation (CV), geometric mean, median, minimum, and maximum.

Additional subject listings including case report form (CRF) data and derived outcomes from the data may be presented.

Baseline Definition

The baseline for plasma AGT concentration from Attoquant will be defined as the average of all values prior to the first dose of Study Drug. The baseline for all other assessments will be defined as the last non-missing measurement prior to the first dose.

Analytical Visits

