3.2.3. Handling of Missing Data

Unless otherwise specified, missing values will not be imputed.

Patients with missing data for a scheduled assessment time point will be excluded from the summary for that time point.

Number of patients with missing data and missing data related to COVID-19 public health emergency may be provided.

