3.3. Primary Analysis

3.3.1. Primary Efficacy Analysis

The primary analysis will be the comparison of change from Baseline to Study Day 85 (Study Week 13) in seated automated office SBP between each ISIS 757456 treatment dose group and pooled placebo group in the PPS. The data will be analyzed as described in Section 3.2.1. Least square mean (LSM) estimated treatment difference with 95% CI and p value will be provided. Additional MMRM analysis will be conducted to assess the treatment effect.

Additional covariates, such as baseline characteristics, may be considered, in the comparison statistical modeling for exploratory analyses.

Additional analysis summary based on the FAS will also be provided.

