3.3.2. Sample Size consideration

Approximately 150 patients will be stratified and randomized to 1 of 2 dose cohorts in 1:1 ratio (Cohort A or Cohort B). Within each dose cohort, patients will be further randomized to receive ISIS 757456 or placebo in a 2:1 ratio.

With the assumptions of mean seated automated office SBP reduction difference of 8 mmHg between an ISIS treated group and pooled placebo with the common standard deviation of 13 mmHg, there are at least 86 eligible patients (n = 43 for an ISIS 757456 treated group and n = 43 for pooled placebo) are needed to provide approximate 80% of power to demonstrate the mean difference between an ISIS treated group and pooled placebo by ANCOVA with the two-sided significant level of 0.05. Additional patients are included while considering an estimated approximate 10% drop-out rate.

The overall type I error rate is controlled at 0.1 level, two-sided.

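### The supportive SBP MMRM may leave unstructured covariance on grounds of fit, and the only alternative named, AR(1), can give a Day 85 interval that is too narrow and only a partial dropout correction

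*Combined protocol and SAP*

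**What the plan says.** The primary analysis is an ANCOVA of SBP change at Day 85 in the per-protocol set (SAP 3.1 and 3.3.1). SAP 3.2.1 makes the MMRM optional in general, but SAP 3.3.1 commits to it for the primary endpoint: "Additional MMRM analysis will be conducted to assess the treatment effect".

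SAP 3.2.1 specifies the model as follows. Visit is categorical, and besides visit and the stratification factor, "treatment received, baseline measure, and treatment-by-visit interaction will be included in the model". The covariance is unstructured at first. Then: "Other covariance structures, such as first-order autoregressive covariance structure based on the assumption of the measurements over time are expected to be correlated" are permitted if model fit suggests it.

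The SAP gives no fit criterion, non-convergence trigger, ordered list, structure with visit-specific variances, degrees-of-freedom method or robust standard error. It does not say whether the model ends at Day 85 or runs to Day 169, nor which analysis set it uses.

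The schedule sets the size of the matrix. SBP is taken weekly through treatment, and protocol 3.4.3 adds: "Patients are to return to the Study Center for Post-Treatment visits on Study Days 85, 92, 106, 120, 148, and 169". On missing data, SAP 3.2.3 says: "Unless otherwise specified, missing values will not be imputed".

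**The concern.** With 12 or 17 visits, an unstructured matrix is large for this sample, so the permitted change may well be used. Which structure results would depend on a criterion chosen after unblinding.

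The named alternative carries two strong assumptions. One variance for all visits means that Day 85 takes its precision from an average over visits. A correlation that decays to zero means that the early readings of a patient who leaves say almost nothing about Day 85.

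Because missing values are not imputed, the Day 85 ANCOVA leaves out patients without a Day 85 value. The MMRM is the only planned Day 85 SBP estimate that draws on their earlier readings. At stake are the interval and the dropout handling of the analysis that readers will set beside the primary result.

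**Working it through.** **Step 1: the plan's own figure.** SAP 3.3.2 assumes a "mean seated automated office SBP reduction difference of 8 mmHg between an ISIS treated group and pooled placebo", a common SD of 13, testing "by ANCOVA with the two-sided significant level of 0.05", and says that 43 + 43 patients "are needed to provide approximate 80% of power". Normal approximation: n = 2(1.960 + 0.842)² × 13²/8² = 41.5, so 42 per group. The t-test power is 79.6% at 42 and 80.5% at 43. With 10% dropout, 43/0.9 = 48 per group, or 144 in all, against about 150. The figure reproduces. The SD of 13 is the only one given; there is none by visit.

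**Step 2: is a change of structure likely?** Day 8 to 85 has 12 visits, so 12 × 13/2 = 78 parameters. Day 8 to 169 has 17 visits, so 17 × 18/2 = 153. AR(1) has 2. Patients number about 150, or 150 × 0.9 = 135 after dropout.

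Assume that the residual correlation between two visits is 0.4 + 0.3·exp(−days/30). For SD patterns from constant 13 to 9 rising to 13, unstructured improves −2logL over AR(1) as follows:

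| Visits | Gain | AIC penalty | BIC penalty (n = 135) |
|---|---|---|---|
| 12 | 275 to 318 | 2 × 76 = 152 | 76 × 4.905 = 373 |
| 17 | 463 to 551 | 2 × 151 = 302 | 151 × 4.905 = 741 |

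AIC keeps unstructured and BIC picks AR(1). The unstated criterion decides.

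**Step 3: the Day 85 interval.** With arm-by-visit means and complete data, the Day 85 estimate is the difference in means under any covariance, so only the standard error changes: SE = SD × √(2/n). AR(1) uses a variance close to the average over visits. Take 13 as the residual SD at Day 85.

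- Let SD rise linearly from 10 at Day 8 to 13 at Day 85. The average variance over 12 visits is 100 + 30 + (9/121)(506/12) = 133.1, so SD 11.54. The ratio is 11.54/13 = 0.888.
- With 45 per arm, SE is 2.43 instead of 13 × √(2/45) = 2.74. The half-width is 4.77 instead of 5.37 mmHg.
- Over 17 visits, with SD 13 after Day 85, the average variance is (12 × 133.1 + 5 × 169)/17 = 143.7, so SD 11.99 and a ratio of 0.922. The fitted AR(1) gives 0.920.

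Fitting AR(1) to each assumed covariance gives these ratios of model SE to true SE; non-coverage is 2[1 − Φ(1.96 × ratio)]:

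| SD, Day 8 to Day 85 | 12 visits | 17 visits |
|---|---|---|
| 13 to 13 | 1.00 (5.0%) | 1.00 (5.0%) |
| 11 to 13 | 0.925 (7.0%) | 0.946 (6.4%) |
| 10 to 13 | 0.888 (8.2%) | 0.920 (7.1%) |
| 9 to 13 | 0.853 (9.5%) | 0.895 (7.9%) |
| 14 to 13 | 1.039 (4.2%) | 1.028 (4.4%) |

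A separate calculation with 10% dropout and four other correlation patterns gave similar results for SD 10 to 13: coverage about 92.2% (12 visits) and 93.1% (17 visits).

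**Step 4: visit spacing.** Gaps are 7 days from Day 8 to Day 92, then 14, 14, 28 and 21. If correlation decays with calendar time, SD is constant and all 17 visits are used, the AR(1) SE at Day 85 is 2.732 against a true 2.728 (weekly correlation 0.7), or 2.704 against 2.692 (0.9). The error is at most 0.5%.

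**Step 5: dropout.** AR(1) predicts a missing Day 85 value from the last reading alone, weighted by ρ to the power of the number of visits between. The fitted ρ is 0.64. For a patient last seen seven visits earlier (Day 36) the implied correlation is 0.64⁷ = 0.04; the assumed one is 0.4 + 0.3·exp(−49/30) = 0.46. With a true difference of −8 mmHg and patients with high SBP leaving:

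| Dropout starts | Complete case | AR(1) | True covariance | Share recovered |
|---|---|---|---|---|
| Day 8 | −7.2 | −7.5 | −8.0 | 0.3/0.8 = 38% |
| Day 64 (11% placebo, 6% active) | −7.6 | −7.9 | −8.0 | 0.3/0.4 = 75% |

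If the true correlation is itself AR(1) in time, the AR(1) bias is about 0 to 0.2 mmHg, close to simulation error.

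**The case against.** The case against is substantial, and most of it limits the point.

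- **AR(1) is an example.** Unstructured comes first. A reader might infer that AR(1) is the fixed fallback; the text does not say so, and under AIC unstructured would be kept.
- **Spacing.** A reader might blame the 7- to 28-day gaps. The documents do not support that for Day 85: visits are weekly through Day 92, and step 4 shows almost no effect.
- **The SD pattern is assumed.** The plan gives one SD. With constant SD the AR(1) interval is right, and with falling SD it is slightly wide.
- **Analysis set.** The PPS requires at least 10 of 12 doses, so its patients are dosed to at least Day 64. There AR(1) removes most of the bias, and the remaining 0.1 to 0.2 mmHg is small against an SE of about 2.7. Patients who stop treatment are also meant to stay in follow-up (protocol 6.1.2 and 8.8), so stopping drug need not mean a missing Day 85 value.
- **Consequence.** The MMRM is outside the testing sequence in SAP 3.4.2, and SAP 3.2.1 does not call it a missing-data check.

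All of this stands. What remains is that the SAP commits to this model for the primary endpoint and leaves its covariance to a later choice by fit, with a poor candidate as the only one named. SAP 3.2.1 also assesses efficacy on the FAS, which needs only one post-baseline SBP value, so early dropout can enter an FAS version of the model.

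**Conclusion.** The point holds as a low-cost correction to a supportive analysis. If AR(1) is used and residual SD rises from 10 to 13 mmHg by Day 85, the Day 85 SE is about 8% (17 visits) to 11% (12 visits) too small and coverage is about 92% to 93%. The cause is the single variance. If correlation does not decay to zero, AR(1) recovers only about a third to 40% of the bias from outcome-dependent dropout that begins early. That matters mainly for the FAS and is small in the PPS. Sizes rest on assumed SD, correlation and dropout patterns, because the documents give none by visit.

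A reader might infer that the trial's type I error is inflated to 6% to 9%. It is not: the primary ANCOVA does not use this covariance, and the percentages above describe interval coverage in the MMRM.

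**What to change.** In SAP 3.2.1:

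1. Estimate the Day 85 effect from an MMRM on visits Day 8 to Day 85 only (12 visits, 78 covariance parameters), and state the analysis set.
2. Add the baseline-by-visit interaction, since the listed terms hold the baseline slope equal at all visits. Its effect was not quantified here.
3. Use unstructured covariance with Kenward-Roger.
4. Only on non-convergence, move in a fixed order to heterogeneous Toeplitz, then heterogeneous compound symmetry, with sandwich standard errors. Both allow visit-specific variances and neither forces correlation to decay to zero. Sandwich errors repair the interval but not dropout bias, so the choice of structure still matters.
5. Delete homogeneous AR(1) and selection by fit.
6. For any model that includes the post-treatment visits, also require visit-specific variances. Plain spatial power on study days would handle the spacing but keeps the single variance and the decay to zero.

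The cost is SAP wording and a few lines of code, with slightly fewer degrees of freedom and a slightly wider interval than AR(1).
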